In UPWARD, UPWARD Extension and UPWARD-S, if suicidality is endorsed with a score of greater than 1 on EPDS item #10 or PHQ-9 item #9 or on any of the self-report questionnaires (such as the SITBI or CCM), subjects will be prompted to complete the CS-S to assess risk of suicidality. Study subjects will also be given the national suicide [contact]) and informed that answers to online questionnaires are not monitored in real time. A positive score on questions 3, 4, or 5 on the CS-S, indicating intention or plan for suicidality, will prompt a safety call by study physicians. Suicidality expressed during the course of clinical or qualitative interviews, either through discussion, endorsement of the suicidality item on the MINI mood module, endorsement of items 3, 4, or 5 on the suicidality module of the MINI, or via scoring >2 on the MADRS item 10, will prompt study staff to complete the CS-S with the participant. A positive score on items 3, 4, or 5 of the CS-S administered by staff will also prompt a safety call by study physicians. In addition, subjects will be told by study staff to call their community providers and go to their nearest emergency room. Endorsement of items 3-5 on the CS-S prompting a physician safety call has been the threshold used in previous studies at the collaborating site (University of Colorado Boulder). As this is a community-based study with collaboration from community physicians, these providers dictate treatment. We will notify community providers directly via phone or fax within 24 hours from report of positive scores on CS-S items 3-5.

VI. BIOSTATISTICAL ANALYSIS

Preliminary Analyses: Differences between the MMB and UC in demographic characteristics and depression related characteristics (e.g., symptom severity, comorbidity) will be assessed using Chi-square test for binary variables, Cochran Mantel Haenszel tests for categorical variables, and t-tests for continuous variables. Variables that show significant group differences and predict outcome will be entered in analyses as covariates; AD exposure will be included as a covariate. All participants will be considered evaluable for analysis (intent-to-treat sample). Significance levels will be evaluated at $p < .05$, and effect sizes reported.

Analysis for Specific Aim #1: To test the relative risk for depressive relapse and reduction of symptom burden between women randomized to digital MMB or UC.

For the analysis of rates of relapse, we will examine time to relapse as rated by the MINI during pregnancy and across the 6-month postpartum follow up using survival analysis. Survival rates will be compared using Cox proportional hazard regression and illustrated in Kaplan-Meier curves (Collett, 1994). However, time to attrition is a competing risk that can be related to time to relapse. We will adopt the subdistribution hazard model (SHM) developed by Fine and Gray to account for the possible non-independence of the censoring mechanism.²⁵

For the continuous outcomes, we will use Hierarchical Linear Models (HLM) as our primary analytic model, which will compare change over time between groups on depressive symptom burden using the PHQ-9. HLM is flexible with respect to the nature of change over time (i.e., linear, piecewise linear, loglinear, etc.), and will accommodate the within subject correlation through the inclusion of random effects at the patient-level, accounting for the patient-to-patient deviations. Pattern-mixture models²⁶ will be used to assess whether important estimates (i.e., intervention effects) are dependent on missing data and to provide overall estimates of effects by averaging over the various missing-data patterns.

Analysis for Specific Aim #2: To explore the specific benefit of MMB relative to AD discontinuation and questions regarding personalization that are of strong interest to pregnant women and their healthcare providers.

H2a: Comparison of MMB to UC among women who discontinue AD: Our analysis will be the same as H1 with both the time-to relapse and continuous outcome models. We predict that rates of relapse and symptom burden among women randomized to MMB who discontinue AD will be significantly superior to those randomized to UC who discontinue AD.

H2b: Treatment Selection Algorithm: We predict that the use of a treatment selection algorithm will differentiate two profiles of women based on pre-treatment characteristics (those who are optimally suited to discontinue AD and engage MMB to minimize their risk of relapse, and those who should continue AD to minimize risk of relapse) and that women who are randomized to the algorithm indicated approach will have significantly lower risk of relapse and symptom burden than women who are randomized to their algorithm contraindicated approach.

Analysis for Specific Aim #3: To test the extent to which digital MMB engages putative targets.

To test target engagement, we will use the same HLM methods described above to compare differences between MMB and UC in change in the putative targets during the intervention period. To test target validation, we will use recent statistical developments that apply formal causal inference concepts to mediation analyses. Causal mediation approaches address violations of the assumption of sequential ignorability (e.g., no confounding/randomization of the mediator) that is required for unbiased estimates of the M (mediator) \rightarrow Y (outcome) relationship. Addressing the issue of sequential ignorability yields unbiased estimates of the natural direct effect (NDE = the non-mediated effect of reduction of depressive related outcomes) and the natural indirect effect (NIE = the component of the intervention that seems to proceed through the respective mechanisms), with Total Effect = NDE + NIE.²⁷ A high NIE indicates that the subsequent outcomes are mediated through time-lagged mechanisms improvements. We have experience implementing these models which fall under the classification of marginal structural models (MSM), principal stratification (PS), structural nested mean models (SNMM), and rank preserving models (RPM),²⁸⁻³⁰ which we will apply for each putative target individually. Sensitivity analyses will be implemented using approaches outlined by Ding and VanderWeele.³¹

Power Analysis for Specific Aim #1: To test the relative risk for depressive relapse and reduction of symptom burden between women randomized to digital MMB or UC.

For the analysis of rates of relapse, in our efficacy study of MBCT,³² pregnant women who received MBCT evidenced approximately 30% lower rate of relapse than UC. In estimating the difference in relapse rates between MMB and UC, accommodating the sample size required to address Aim 2, N = 600 participants is required for randomization. With N=600, we have 95.5% power to detect a 20% difference in relapse rates (which is smaller than what we observed in our efficacy study) and allowing for 30% attrition, which is higher than attrition in our efficacy study of MBCT with pregnant women (15%) and lower than attrition in our digital delivery of MBCT work (approximately 40%).

For the continuous outcomes, using the method described by Ahn et al. to derive formulas for power estimation of linear mixed models,³³ power calculations can be made for repeated measures designs under specified assumptions. Based on a sample size of 300 per group, assuming 30% attrition for a total of 175 per arm randomized, with an alpha-level at 0.05 based on a 2-tailed test, assuming a within correlation of 0.5, we have power of 86.5% to detect an effect size of .25. Varying the effect size, we have 95.7%, 99.0%, and 99.8% power for effect sizes of 0.3, 0.35, and 0.4 respectively, which are much smaller than the d=0.70 effect size

observed in our efficacy study of MBCT with pregnant women,³⁴ indicating that we are sufficiently powered.

Power Analysis for Specific Aim #2: To explore the specific benefit of MMB relative to AD discontinuation and questions regarding personalization that are of strong interest to pregnant women and their healthcare providers.

H2a: Comparison of MMB to UC among women who discontinue AD: Anticipating balance across the 4 cells (randomized to MMB or UC; choice of discontinue AD or maintain AD), with approximately 300 participants across the two cells of interest, we have 82.8% power to detect a 23% difference in relapse rates with 30% attrition, which is smaller than what would be expected comparing the relapse rates among women who received MBCT (19%) in the [name] et al. study of MBCT with pregnant women³² to the rate of relapse among women who discontinued AD during pregnancy (66%) in the Cohen et al. prospective study¹⁰).

H2b: Treatment Selection Algorithm: Although there has been growing interest in trials focused on estimation of an optimal personalized treatment strategy,³⁵ there are no standard formula since the outcome of interest, the personalized treatment regimen, is not a measurable outcome as in typical power derivations.³⁶ Laber and colleagues provide a method for sizing such a trial, which they apply to their fertility (time to pregnancy) data example.³⁷ In their setting, they estimated a sample size of 280 was needed to yield 80% power for superior coverage with 9 terms (including main effects and interaction terms) with an interval width of 0.38. Based on a slight modification of width to 0.40, we estimate a sample size of 250 is needed with 9 terms. Based on our prior data,¹⁰ we project that 50% of participants randomized to MMB will discontinue AD (n=150) and 50% of participants randomized to UC will continue AD (n=150); thus, our randomized sample (N=600) should be sufficiently powered to build a model with up to 4 moderator variables (the number identified in our preliminary data). We will conduct PAI analysis with the SAS software procedure PROC QLEARN.

Power Analysis for Specific Aim #3: To test the extent to which digital MMB engages putative targets. Fritz et al. derived sample size requirements to guarantee 80% power.³⁸ With a small to medium effect for treatment on the mediator and a small to medium effect for treatment on outcome, covarying the mediator, the sample size for 80% power is 224 patients; therefore, our proposed sample, even with as much as 30% attrition is more than sufficient to test mediation with 80% power.

VII.. RISKS AND DISCOMFORTS

Participation in this study is not anticipated to confer risk to the fetus greater than that expected in normal day-to-day activity. Clinical studies of MBCT, including studies with non-pregnant women, have been conducted and indicate no potential risks to pregnant women or fetuses. Subject burden for participation occurs for approximately 12 months depending on gestational age at enrollment and includes the initial baseline interview, post-intervention interview, third trimester interview, 3-month postpartum interview, and 6-month postpartum interview, as well as monthly questionnaires. Participants in the UPWARD MMB condition will additionally receive telephone/email coaching through the MMB program during the 12-week intervention period. However, participants in UPWARD Extension will not complete any prospective clinical interviews beyond the baseline call, and will only be followed longitudinally through self-report surveys through 3 months postpartum. There are no known psychological, social, economic or legal risks for participation or completing the questionnaires or interviews. However, it is possible that participants may experience temporary and mild psychological discomfort as a result of thinking about painful aspects about their lives and relationships with others as a result

of survey questions. For instance, examples of the most personal and sensitive questions include asking about abuse of alcohol or illegal drugs and history of suicidality. The topics in the MMB program may evoke painful or uncomfortable feelings (e.g., when directing attention to self-critical thoughts); however, these risks are no greater than what would occur in daily life. Patients will be advised that all questions are voluntary.

We will include detailed information about possible risks in the study fact sheets, which illustrate the most sensitive types of questions about which subjects will be asked on the questionnaires and as part of the MMB intervention, should they be randomized to that condition. Participants also will be instructed that they may discontinue participation in the study or the MMB intervention, and/or choose not to complete web-based assessments at any time by informing the research team by phone or email.

It is possible that participants may experience injury or discomfort when engaging in the mindfulness stretching/yoga practices at home. The mindfulness and yoga practices included in the MMB intervention have been specifically tailored to pregnant and postpartum women. A description of the mindfulness/yoga components will be included in the consent form so that individuals are informed about the nature of the practices, and the digital program will instruct participants not to engage in any exercise or practice they think will be harmful to their health or well-being.

Usual care will not be constrained for any study participants, including those randomized to MMB. Usual care will be augmented by ongoing study assessments and the provision of feedback to participants based on their responses to the PHQ-9, EPDS, and clinical interviews (e.g., “Your answers suggest that you are having significant symptoms of depression. We recommend that you talk with your prenatal care provider about whether treatment might help”). Usual care also will be augmented by ongoing availability of study physicians with perinatal psychiatric expertise for community clinicians treating women with pharmacologic treatment. All treatment decisions, including use of medications and treatment of emergent symptoms, will be managed by the participant’s community prescriber who is not a study investigator. Participants in the UC group will be followed naturally, and no clinical interventions will be made by study investigators. The probability and magnitude of harm or discomfort associated with participation in this arm of the study is not anticipated to be greater than that encountered in daily life.

Participants also may feel inconvenienced by the time required to complete the research procedures. Participants will be informed about the expected duration of each assessment time point and MMB practice sessions for participants in that arm, and we have designed the assessment procedures to minimize burden on participants. Participants in the parent UPWARD Study will receive a total of \$175 for completing the study assessments in compensation for their participation. Those who choose to complete the UPWARD Baby timepoint at 12 months postpartum will be compensated an additional \$20. Participants in UPWARD Extension will receive a total of \$140 for completing the study assessments. Participants in UPWARD Supplement Arms 1a and 2 will be compensated \$200 for their participation in the study (\$25 more than parent UPWARD study to compensate for participation in qualitative interviews and additional self-report questionnaires). Providers that participate in UPWARD Supplement Arm 1b will be compensated \$75 for their participation in the qualitative interview. Participants in UPWARD Supplemental Arm 1c will be compensated \$25 for completing the online survey, which will be texted to them as a gift card code on the mobile phone number they provide at consent. Participants assigned to the MMB condition also will receive the intervention at no cost. Participants who terminate participation early will be paid a prorated amount depending on the

length of their participation, and if participation in the study is ended by the investigator, participants will receive a prorated amount depending on the length of their participation.

Subjects who have a history of depression will be included in the proposed trial and therefore the recurrence or exacerbation of mood symptoms during study participation is a possible but expected risk. Suicidal ideation reported in phone interviews or self-report questionnaires over the course of study will be addressed in a timely manner by study staff who can refer to the community provider or emergency services. Specifically, we will carefully monitor depressive symptoms, including suicidality, throughout the study, using the PHQ-9³⁹ and EPDS completed at regular assessment points via REDCap, and on the real-time phone contacts and interviews administered by MGH study staff, which assess depression course and relapse.

If a participant scores greater than or equal to 15 on the PHQ-9 or greater than or equal to 12 on the EPDS, the online data collection and management system (REDCap) will automatically provide participants with contact information for national mental health crisis resources and for the research study team. Study investigators will be notified immediately via an algorithm programmed into REDCap. In the UPWARD parent trial and UPWARD-S Arms 1a and 2, study staff at MGH will initiate a clinical response by phone call to assess clinical status and suicidality as soon as possible within 24 business hours of report. The score of 15 is suggested as the threshold for moderate depression.³⁹ Additionally, we will monitor specifically responses to the suicide item (#9) on the PHQ-9: 'Thoughts that you would be better off dead or hurting yourself in some way.' and the suicide item (#10) on the EPDS: 'The thought of harming myself has occurred to me' for all study participants. If a participant endorses either of these items with a score of 1 or greater, REDCap will automatically route participants to fill out the Columbia Suicide Severity Rating Scale (CS-S) and provide participants with contact information for national mental health crisis resources and for the research study team. Study investigators and staff will be automatically notified by the REDCap system for a positive score on questions 3-5 of the CS-S in order to provide outreach as soon as possible within 24 hours and assessment of the patient by a study doctor. In UPWARD-S, endorsement of current suicidal ideation on the SITBI or CCM item (#11) will also automatically route participants to fill out the CS-S. Any endorsement of items 1-5 of the CS-S will prompt administration of the full CS-S to capture duration and intensity of suicidal ideation and/or behaviors. Furthermore, any participant who misses a scheduled assessment point will be contacted immediately by study staff. Study staff will continue to try to reach participants until a participant indicates that they no longer wish to be contacted or the participant has reached six months postpartum by their estimated date of delivery, whichever comes first. Throughout the study, all participants also will be encouraged to contact the study staff at the first sign of increased depression.

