around pregnancy stage or topic, will also be used to recruit women meeting the inclusion criteria. BabyCenter's Community managers can post invitations to participate in a research study as a message in the relevant community boards, and women who are interested can click through to a short eligibility survey. As the majority of BabyCenter users are on mobile phones, these recruitment sources can be accessed through both desktop and mobile devices. Ineligible participants who fill out the online eligibility survey via BabyCenter will also have the option of providing their contact information to be contacted about future research opportunities either at the Center for Women's Mental Health or the University of Colorado Boulder.

IV. SUBJECT ENROLLMENT

UPWARD Study

Participants will be linked to a recruiting survey on University of Colorado Boulder's REDCap site describing the study including length, the number of assessments, and incentives, and will proceed to answer screening questions aimed at determining initial eligibility. At this point, individuals can continue with the online screening or opt out. Following identification of potential study participants, women will be given the option to either provide contact information or directly contact the research team for enrollment. Potential study participants will also be given the option of signing up for a screening call using Calendly, a secure online scheduling tool. MGH study staff trained to assess perinatal women will confirm, by phone interview, inclusion and exclusion criteria, address any questions, and review the online study fact sheet.

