UPWARD and each UPWARD Supplemental Arm will have a unique study fact sheet. The online study fact sheet will accurately describe the general goals of the study and the nature of the participant's role in the study. Participants will be given the ongoing opportunity to ask any questions regarding confidentiality, participation schedule, or any other aspect of the study in the first call with the MGH team and in all subsequent contacts with study team members. After reading the study fact sheet, study staff will obtain verbal consent for participation. In addition, participants will review key points of the study with study staff, will be provided with contact information and encouragement to contact study staff members with questions via email or phone, and will be encouraged to print and retain personal copies of the study fact sheet. Consented subjects will be sent a copy of the phone consent document. This consent form will include a summary of privacy policies and date of consent. Individuals who do not provide verbal consent will be informed that it is not possible for them to participate in the study and we will provide them with a list of links to depression information websites.

[figure not shown]
To maintain concealment, assignment will occur following the baseline assessment by telephone interview with the MGH team. Assignments will be generated using a random number table with equal probability of assignment to each group in blocks of four, which will guarantee balance for every four subjects. Randomization to study arm will be stratified based on number of prior episodes, antidepressant medication status (on medication or having discontinued at time of randomization), and baseline depressive severity based on PHQ-9 score. Women will be randomly assigned to receive MMB ($n = 300$) or UC ($n = 300$).

Study staff will also obtain contact information for community providers and consent from study participants to be in touch with these providers. This contact information will be used to send a letter describing the study and providing the consult line and availability of study doctors for questions. Additionally, we will reference the MGH Center for Women's Mental Health's website, www.womensmentalhealth.org, as a perinatal resource center that provides evidence-based safe practices for both the study participant and their clinician during pregnancy.

UPWARD Supplemental Arms

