The final 100 participants in the UPWARD sample of 600 individuals will participate in an abbreviated version of the UPWARD procedures. These 100 women will be recruited via the same platform of BabyCenter, screened and enrolled based on the same entry criteria, and similarly randomized to the MMB intervention or Usual Care. However, the only differences will be that these final participants in this group of 100 who are randomized to the treatment group will not receive the coaching that is typically involved in the MMB intervention. This will further investigate our research aims to assess the extent to which this modified version of MMB is still an effective means of preventing depressive relapse in a perinatal population. Moreover, these final 100 participants will not receive any follow-up clinical interviews or relapse determination calls after the initial screening and baseline calls. Participants will be randomized after the baseline call, either through a phone conversation or via email. They will instead be prospectively followed through 3 months postpartum via the same battery and schedule of self-report questionnaires given to the other UPWARD participants through this timepoint. If any participant endorses items 3, 4, or 5 on the C-SSRS via these self-report questionnaires, the same suicidality safety protocol will be triggered as outlined below. The information about the delivery and newborn outcomes that would typically be collected during the 3 months postpartum interview will now be administered as a self-report survey with the rest of the questionnaires for this timepoint.

Table 2. UPWARD Extension Measurement Schedule

UPWARD Study	Baseline	M1	W6	M2	Post-Intervention	M3	M4	M5	3T	M6	M7	M8	3PP
MINI full	x												
MINI mood	x				x				x				x
MADRS	x				x				x				x
EPDS	x	x	x	x		x	x	x	x	x	x	x	x
PHQ-9*	x	x	x	x		x	x	x	x	x	x	x	x
CS-S**	x												
CGI	x				x				x				x
PGI	x	x	x	x		x	x	x	x	x	x	x	x
GAD-7	x	x	x	x		x	x	x	x	x	x	x	x
PSS-10	x					x			x				x
WHODAS 2.0	x					x			x				x
CSQ-8 (UC)	x					x							
CSQ-8 (MMB)						x							
CTQ	x												
PROMIS	x												
FFMQ	x		x			x							
RRS	x		x			x							
SCS	x		x			x							
SSQ-SF	x					x							x
RSQ-MEP	x												
LEL	x												
LEIDS-R	x		x			x							
EQ	x		x			x							
CSI	x												
AToM	x					x			x				x
PSA	x		x			x			x				
PSQI	x					x							x
Positive Mood Diary	x		x			x							

DPES Joy Subscale	x		x		x					x
CERTS Unresolution Subscale	x									

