MGH physicians with perinatal psychiatry expertise will be available via a consult line for community providers of participants enrolled in the UPWARD Study and UPWARD-S. Throughout the study, they will answer questions regarding psychiatric medications and possible treatment options for individual patients determined by their community provider.

MGH study staff trained in interviewing techniques will administer the baseline, qualitative, post-intervention, third trimester, 3 months postpartum, and 6 months postpartum interviews completed for enrollees in UPWARD and UPWARD-S. Those enrolled in UPWARD Extension will complete only the screening and baseline calls. Participants will then be randomized either over the phone or via email. Baseline clinical instrument results will be reviewed and confirmed by study principal investigators to ensure eligibility. We will send a birth acknowledgement by regular mail, email, or both after delivery, and at periodic times during the study, we will send reminders of study engagement or gifts of nominal value to increase cohort retention.

In the UPWARD Study, in addition to regularly scheduled self-report questionnaires and phone contacts, relapse determination calls will be made to any participant scoring ≥ 15 on the monthly PHQ-9 or ≥ 12 on the EPDS. This relapse determination call will consist of study staff asking about the date of relapse and administering the MINI mood module and MADRS retrospectively to assess depressive symptoms during the time of relapse. If a depressive relapse has already been confirmed via clinical interview with the MINI mood module or the MADRS within a week of completion of self-report answers to either the PHQ-9 or EPDS, no relapse determination call will be made. However, if a depressive relapse is not documented during the clinical interview with the MINI mood module, but follow-up self-report surveys indicate increased depressive symptoms, a relapse determination call will be made.

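### Randomization uses one disclosed block size of four within strata and names no list holder, so up to one assignment in three is knowable to anyone who sees all earlier assignments in a stratum.

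*Combined protocol and SAP*

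**What the plan says.** Section IV (Subject Enrollment, UPWARD Study) describes 1:1 assignment of 600 women from a random number table, "with equal probability of assignment to each group in blocks of four, which will guarantee balance for every four subjects". The list is stratified: "Randomization to study arm will be stratified based on number of prior episodes, antidepressant medication status (on medication or having discontinued at time of randomization"), with baseline PHQ-9 severity as the third factor. No cut-points or number of strata are given. Section V (Aim 2) repeats the scheme for the 40 women in Arm 2.

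On concealment, Section IV says: "To maintain concealment, assignment will occur following the baseline assessment by telephone interview with the MGH team". For the Extension, Section V says: "Participants will be randomized after the baseline call, either through a phone conversation or via email". Neither place says who generates, holds or releases the sequence.

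On roles:

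- **Screening** (Section IV): "MGH study staff trained to assess perinatal women will confirm, by phone interview, inclusion and exclusion criteria".
- **Interviews** (Section V, Prospective Follow-up and Community Outreach): "MGH study staff trained in interviewing techniques will administer the baseline, qualitative, post-intervention, third trimester, 3 months postpartum, and 6 months postpartum interviews".
- **Eligibility sign-off** (same place, directly after a sentence on randomizing Extension participants): "Baseline clinical instrument results will be reviewed and confirmed by study principal investigators to ensure eligibility".
- **Blinding**: Section V (Baseline Clinical Assessment and Depressive Relapse) makes the evaluators blind to condition. Section IX does the same for the MGH staff who give the MINI mood module.
- **Intervention**: Section V (MMB Treatment Protocol) puts oversight of MMB and its coaching at CU Boulder.

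**The concern.** Assigning after baseline stops a woman's own baseline data from being collected with her arm known. It does nothing to hide the arm of the next woman. With a single block size printed in the protocol, past assignments in a stratum always reveal the fourth place of a block, and reveal the third whenever the first two match.

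This matters only if someone who influences entry sees those past assignments. Women and coaches necessarily know the arm, so the information exists in the study. The protocol does not say that screening staff, or the principal investigators who sign off eligibility, are shielded from it.

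Some entry criteria in Section III call for judgement, notably no relapse since the last menstrual period and immediate risk of self-harm. Foreknowledge could affect, even unintentionally, who is confirmed and when. Relapse is the Aim 1 outcome, so selection on relapse-related criteria would bear directly on the MMB versus UC comparison. If eligibility is confirmed after the arm is known, the same route is open whatever the block size.

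**Working it through.** **Inputs.** Block size 4, ratio 1:1, N = 600 and three stratification factors (Section IV); N = 40 for Arm 2 (Section V). The number of strata is not given. I take 8 (2 x 2 x 2) as an assumption and show 4 to 27.

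**1. The plan's own allocation.** 600/4 = 150 blocks, and 150 x 2 = 300 per arm, as stated. With strata, an unfinished block can put each arm off by at most 1, so 8 strata give at most 300 ± 8. The stated arm sizes reproduce.

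**2. Certain knowledge, one stratum, all earlier assignments seen.** There are C(4,2) = 6 equally likely blocks.

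- Places 1 and 2: never known.
- Place 3: known when places 1 and 2 match, 2 of 6 blocks = 1/3.
- Place 4: always known.

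Share known = (0 + 0 + 1/3 + 1)/4 = 1/3 = 33.3%.

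**3. Best guess, same observer.** The chance of a correct guess by place is 1/2, 2/3, 2/3 and 1. For place 3 this is 1/3 x 1 + 2/3 x 1/2 = 2/3. The mean is (17/6)/4 = 17/24 = 70.8%.

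**4. Effect of strata.** For an observer who tracks strata, simulation with N = 600 gives a certain share of 33.0% (4 strata), 32.8% (8), 32.5% (12), 32.0% (18) and 31.5% (27). For Arm 2 it is about 25% (8 strata) or 20.5% (12). An observer who follows only the pooled sequence has no certainty; a simple balance-guessing rule is then right 57.6% of the time with 8 strata.

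**5. Partial sight of earlier assignments.** Suppose each is seen independently with probability k and block starts are known. Certainty needs both members of the matching pair to be seen, so the share is (k²/3 + k²)/4 = k²/3.

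| k | k²/3 | Simulated, 8 strata |
|---|---|---|
| 1 | 33.3% | 32.8% |
| 0.5 | 8.3% | 8.2% |
| 0.25 | 2.1% | 2.1% |
| 0 | 0 | not run |

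**6. Varying block sizes.** The observer sees every earlier assignment and knows the set of sizes but not their order. Ranges come from two simulations, one with 75 women per stratum (600/8) and one with 40,000 assignments.

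| Sizes | Known with certainty | Best guess correct |
|---|---|---|
| 4 only (75 per stratum) | 32.5% | 70.4% |
| 4, 6 | 5.4-5.5% | 69.0-69.3% |
| 4, 6, 8 | 2.3-2.5% | 67.8-68.0% |

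Varying sizes removes certainty and leaves guessability almost unchanged. Only lowering k removes both.

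**7. Order of events.** Section V (Prospective Follow-up) mentions randomization of Extension participants and then, in the next sentence, the principal investigators' review. Section IV ties assignment to completion of baseline and does not mention that review. No sentence fixes which comes first.

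**The case against.** The strongest objection is that prediction requires sight of past assignments, and the protocol blinds the evaluators and the MGH staff who give the MINI. MGH staff conduct both baseline and follow-up interviews, and MMB is run from another site. If that blinding covers everyone who enrols women, nothing is knowable. This stands as a limit on size. It does not close the point, because the documents never say that enrolling staff or the principal investigators are covered, or whether enrolling staff and blinded evaluators are different people.

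A reader might infer that the MGH team that screens also runs the list. The text does not say so. In Section IV the reference to the MGH team can describe the baseline interview alone, and the Extension text names nobody. Section V (Aim 2) does place the Arm 2 qualitative interview, which MGH staff conduct, at or near the randomization call. That suggests that MGH staff may be close to assignment, but not that they hold the sequence.

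A reader might also call the trial open-label without qualification. The documents do not use the term, and assessment of relapse is to be blind.

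Eligibility is also partly protected. The PHQ-9 limit is numeric, first screening is an online survey, interviewers must reach a weighted kappa above .80, and stratification limits imbalance on three prognostic factors. This narrows the room for selection without removing the judgement-based criteria.

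**Conclusion.** The point holds as a minor weakness in concealment and in reporting. The block size is fixed and disclosed, timing is the only stated safeguard, list custody is unstated, and eligibility sign-off is not ordered relative to randomization.

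The 33% (and the 71% best guess) is a ceiling. It assumes an observer who knows every earlier assignment in the stratum and where blocks begin. It is about 8% if half are seen, about 2% if a quarter are, and zero if enrolling staff are blind to them. It would be wrong to infer that a third of assignments were in fact foreseen, or that the comparison is biased: the documents give no evidence of either, and no size of bias can be derived from them. The ceiling depends little on the assumed number of strata for N = 600.

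**What to change.** For women not yet randomized, in order of value:

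1. State who generates, holds and releases the sequence, choosing someone not involved in screening, and keep enrolling staff blind to past assignments. State whether enrolling staff are separate from the blinded interviewers.
2. Release the arm through REDCap, which the study already uses, only after the principal investigators' eligibility confirmation is entered.
3. Load a new list with concealed, randomly varying block sizes (for example 4, 6 and 8) within the existing strata, and keep the sizes out of staff-facing documents.

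Apply the same to Arm 2. For women already randomized, the list cannot be changed, but documenting who had custody and the actual order of confirmation and assignment would help readers judge the result.

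The cost is a new list and a REDCap setting. An unfinished block of 8 can leave a stratum up to 4 apart, against 2 with blocks of four, so balance in small strata may be slightly looser. The documents do not say how many women remain to be randomized at this version, though Section VII shows that some already had been, so the benefit of the new list may be small.
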